Investigation of subject characteristics	Х	Х														
Enrollment		Х														
Body weight*3	Х				X *15		Х	Х	Х	Х		Х	Х		Х	Х
Height	Х															
Hospitalization *4					Х						2	X			Х	
Investigational product (TAS-205/placebo) administration*5			Presc	ription	X *5	$\rightarrow$	$\rightarrow$	$\rightarrow$	$\rightarrow$	$\rightarrow$	$\rightarrow$	$\rightarrow$	$\rightarrow$	$\rightarrow$	X *5	
Medical examination	Х				X *15	Х	Х	Х	Х	Х		Х	Х		Х	Х
Blood pressure, pulse rate, body temperature *6	Х				X *15	Х	Х	Х	Х	Х		Х	Х		Х	Х
Hematology/biochemistry*6	Х				X *15		Х	Х	Х	Х		Х	Х		Х	Х
Endocrinology*6					X *15		Х					Х			Х	(X) *19
Urinalysis *6	Х				X *15		Х	Х	Х	Х		Х	Х		Х	Х
12-lead ECG *7	Х				X *15	Х	Х	Х	Х	Х		Х	Х		Х	Х
Cardiac ultrasonography (echocardiography)*7	Х											Х			Х	Х
Pulmonary function test	Х				X *15		Х		Х			Х			X *17	
Motor function: 6MWD	Х				X *15							Х			X *17	
Motor function: time to rise from the floor, Timed 10-m walk/run test, Timed Up & Go test					X *15							х			X *17	
Measurement of muscle volume: skeletal muscle CT					X *15										X *17	
Measurement of muscle volume: BIA*8					X *15		Х	Х	Х	Х		Х	Х		X *17	
Lean body mass *8					X *15		Х	Х	Х	Х		Х	Х		X *17	
Quantitative muscle strength assessments					X *15							Х			X *17	
Urinary tetranor-PGDM/PGEM concentrations,																
urinary creatinine and creatine concentrations, urine				Х		Х					Х	ζ.			х	
weight, and urine specific gravity (pooled urine)*9																
Subject medication diary (investigation of treatment compliance, etc.) *10				Supply	х	$\rightarrow$	$\rightarrow$	$\rightarrow$	$\rightarrow$	$\rightarrow$	$\rightarrow$	$\rightarrow$	$\rightarrow$	$\rightarrow$	х	(X)
Concomitant medication/therapy *11	X	$\rightarrow$	$\rightarrow$	$\rightarrow$	$\rightarrow$	$\rightarrow$	$\rightarrow$	$\rightarrow$	$\rightarrow$	$\rightarrow$	$\rightarrow$	$\rightarrow$	$\rightarrow$	$\rightarrow$	$\rightarrow$	Х
Evaluation of adverse events *11	Х	$\rightarrow$	$\rightarrow$	$\rightarrow$	$\rightarrow$	$\rightarrow$	$\rightarrow$	$\rightarrow$	$\rightarrow$	$\rightarrow$	$\rightarrow$	$\rightarrow$	$\rightarrow$	$\rightarrow$	$\rightarrow$	Х

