# 13.1.3.3 Analysis of the Secondary Endpoints

# 13.1.3.3.1 Efficacy Analysis

The following analyses will be performed in the PPS and FAS:

- (1) 6MWD
  - Summary statistics will be calculated at each time point for each treatment group.
  - A 2-sample t-test will be performed between each treatment group and placebo group at Week 12. This analysis will be performed with and without the LOCF imputation.
  - The time course by each time point will be plotted for each treatment group.
- (2) The following analyses will be performed for each value measured in each motor function test (time to rise from the floor test, Timed 10-m walk/run test, Timed Up & Go test), measurement of muscle volume (skeletal muscle CT, BIA), lean body mass, quantitative muscle strength assessments (hip flexion/extension, knee flexion/extension, ankle extension/flexion), serum CK concentration (only the serum CK concentration during the hospitalization period will be used for the efficacy evaluation), and pulmonary function test (VC, FVC, FEV1.0, FEV1.0%):
  - Summary statistics will be calculated at each time point for each treatment group.
  - Summary statistics for the change from baseline will be calculated, followed by a 2-sample t-test between each treatment group and placebo group at each time point. This analysis will be performed with and without the LOCF imputation.
  - The treatment effect will be estimated using the MMRM.
  - Using the MMRM, the dose relationship will be analyzed with treatment contrasts of (placebo group, low-dose group, high-dose group) = (-2 1 1), (-1 0 1), and (-1 -1 2).
  - The time course by each time point will be plotted for each treatment group.

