Since the present study is positioned as a small-scale early Phase II study with the nature of a pilot study to evaluate the efficacy of TAS-205 in an exploratory manner, the 6MWD test in the study may be performed without the necessity to determine statistical significances. The target sample size, therefore, was not determined statistically. On the premise that the efficacy of TAS-205 will be determined in terms of the numerical trends in an appropriate manner, the sample size was determined from the viewpoint of feasibility. Given the development status of similar therapies to date and the future study plan of TAS-205, etc., it may be difficult to determine the efficacy of TAS-205 appropriately based only on the 6MWD and other evaluations of motor function in the early Phase II study; therefore, other efficacy endpoints, including the evaluations of muscle volume, lean body mass, or muscle strength, were added to these evaluations to ensure comprehensive assessment of the efficacy of TAS-205. In addition, the muscle volume will be evaluated using skeletal muscle CT in the present study. In consideration of the radiation effects, the evaluation will be limited to lower extremities and only 2 time points, before start (baseline period) and at the end (end of the administration period) of investigational product administration, in consideration of number of measurements. For serum CK concentration, unlike the evaluation during the hospitalization period, which involves relatively low patient burden, including physical activities, and rested conditions, the outpatient evaluation may be subject to various effects/confounders during daily activities; therefore, only the values measured during the hospitalization period will be used for the efficacy evaluation.

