- (2) The following analyses will be performed for each value measured in each motor function test (time to rise from the floor test, Timed 10-m walk/run test, Timed Up & Go test), measurement of muscle volume (skeletal muscle CT, BIA), lean body mass, quantitative muscle strength assessments (hip flexion/extension, knee flexion/extension, ankle extension/flexion), serum CK concentration (only the serum CK concentration during the hospitalization period will be used for the efficacy evaluation), and pulmonary function test (VC, FVC, FEV1.0, FEV1.0%): In the analysis of the muscle volume measurement (skeletal muscle CT) in the PPS, the subjects of the reference values will be excluded. See Table 10.1 Method to Derive %MVI (%) for derivation of %MVI (%) of the muscle volume measurement (skeletal muscle CT). In quantitative muscle strength assessments, the maximum values in the measurement without compensation will be used.
  - Summary statistics will be calculated at each time point for each treatment group.
  - Summary statistics for the change from baseline will be calculated, followed by a 2-sample t-test between each treatment group and placebo group at each time point. The data at Week 24 will be analyzed with and without the LOCF imputation.
  - With respect to the above 2 analyses, subgroup analysis will be conducted for the following items.

Subgroup analysis: Presence or absence of the history of steroid use, age category ( $\geq$ 5 years and <7 years, and  $\geq$ 7 years), and baseline 6MWD (<350 m, and  $\geq$ 350 m)

- The treatment effect will be estimated at each time point using the MMRM. The changes from baseline in the values measured at other time points will also be included in this analysis. Covariates will be the assigned group, baseline value, time point, and the interaction term of the assigned group and time point.
- Using the MMRM, the dose relationship will be analyzed at each time point with treatment contrasts of (placebo group, low-dose group, high-dose group) = (-2 1 1), (-1 0 1), and (-1 -1 2). Covariates will be the assigned group, baseline value, time point, and the interaction term of the assigned group and time point.

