#### O LOCF

If the data at the last time point of observation are missing, the data which are not missing and have been obtained immediately before that time point will be used for interpolation, irrespective of whether or not the data are within the acceptable range.

Confidence interval of incidences

The confidence interval of incidences (or incidence rates) will be obtained by an exact method based on F distribution.

The number of subjects in the analysis set is put as N and the number of subjects exhibiting adverse events is put as X. Thus, the incidence (P) and the upper limit ( $P_U$ ) and lower limit ( $P_L$ ) of the exact 2-sided 100(1- $\alpha$ )% confidence interval of the incidence will be estimated by the following formulas. In the case of 95% confidence interval,  $\alpha$ =0.05.

Adverse events

Adverse events will be coded according to MedDRA/J, and Preferred Terms (PT) will be used for tabulation unless otherwise specified. The version of MedDRA to be used will be the newest version available as of the time of data fixation as a rule, but it will be decided by the MedDRA manager.

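### LOCF is specified for skeletal muscle CT, which has no visit between baseline and Week 24, so a missing Week 24 scan is scored as zero change

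*SAP*

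**What the plan says.** SAP 6.2.1(2) covers a set of secondary endpoints that includes "measurement of muscle volume (skeletal muscle CT, BIA), lean body mass, quantitative muscle strength assessments". Their change from baseline is compared with placebo by two-sample t-tests, and "The data at Week 24 will be analyzed with and without the LOCF imputation". Protocol 13.1.3.3.1(2) has the same list and the instruction "This analysis will be performed with and without the LOCF imputation". Neither document exempts CT.

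On CT timing, Protocol 14.1 cites radiation exposure and says that "the evaluation will be limited to lower extremities and only 2 time points, before start (baseline period) and at the end" of administration. The row "Measurement of muscle volume: skeletal muscle CT" in Protocol Table 1 agrees: it is marked at baseline and Week 24 and nowhere between.

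The LOCF rule is in SAP 8.3. When the last time point is missing, "the data which are not missing and have been obtained immediately before that time point will be used for interpolation", and this holds "irrespective of whether or not the data are within the acceptable range". It does not say whether the carried value must be post-baseline.

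Three other provisions decide who is affected:

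- FAS entry (SAP 4.1) needs one efficacy evaluation of any kind after dosing starts.
- The PPS (SAP 4.1) drops subjects not evaluated for the primary endpoint, the Week 24 change in 6MWD.
- The discontinuation test (Protocol Table 1, note 16) covers safety endpoints, and Protocol 10.3 carries the same qualifier, so no CT is required when a boy stops early.

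**The concern.** LOCF is meant to use the last on-treatment information about a subject. For CT no such information is scheduled: the only planned value before Week 24 is the baseline scan, so the imputed change is baseline minus baseline.

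Protocol 1.1 describes DMD as progressive after about 4 to 5 years of age. A zero is therefore favourable relative to the expected course. It may be given to boys who left because they were declining, since Protocol 4.3 withdraws those who need walking aids during the efficacy evaluations.

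CT also carries some weight. Protocol 14.1 says that motor function tests alone may not settle efficacy and adds muscle volume, lean body mass and muscle strength for that reason. The CT LOCF comparison also feeds the subgroup tables in SAP 6.2.1(2).

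**Working it through.** **No plan figure to reproduce.** The documents give no effect size, SD, dropout rate or expected CT change. The sample size (33, or 33/3 = 11 per group) was set by feasibility.

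**Step 1: what the rule yields.** Two CT time points minus one baseline leaves one post-baseline scan. If it is missing, the preceding value is baseline, so imputed change = baseline - baseline = 0. If LOCF were read as post-baseline only, nothing could be carried and the CT runs with and without LOCF would be identical. For CT the instruction is either biased or empty.

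**Step 2: who is affected.** BIA and lean body mass are scheduled from Day 6 (Protocol Table 1), so a boy who stops early will usually be in the FAS without a post-baseline CT. The PPS should hold few such boys, because CT and the primary endpoint are due at the same evaluation. A boy with a Week 24 6MWD but no usable scan would remain in it.

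**Step 3: other endpoints.** 6MWD, the timed tests and muscle strength have a Week 12 visit, so baseline is carried only when a boy has no Week 12 value. BIA, lean body mass, pulmonary function and CK have further post-baseline measurements before Week 24. Guaranteed carry-forward of baseline is specific to CT.

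**Step 4: size of the bias.** Let m be the fraction of an arm with a missing scan and mu the true mean change, with missingness at random. The LOCF arm mean is (1 - m) x mu.

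- Equal missingness: a true difference is multiplied by 1 - m, that is 10/11 = 91%, 9/11 = 82% or 8/11 = 73% for 1, 2 or 3 missing per arm.
- No true effect: the spurious difference (active minus placebo) is (m_placebo - m_active) x mu. With no scans missing on placebo, and assumed values of mu in points (for example on the %MVI scale):

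| Assumed mu, both arms | 1/11 missing on active | 2/11 | 3/11 |
|---|---|---|---|
| -2 | +0.18 | +0.36 | +0.55 |
| -5 | +0.45 | +0.91 | +1.36 |
| -8 | +0.73 | +1.45 | +2.18 |

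**Step 5: effect on the t-test.** Simulation with 40,000 runs, 11 per arm, two-sided 0.05, assumed mean change -5 in both arms, so every rejection is false:

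| Missing (placebo, active) | LOCF, SD 3 | LOCF, SD 5 |
|---|---|---|
| 0, 0 | 5.0% | 4.9% |
| 0, 2 | 8.1% | 6.4% |
| 0, 3 | 13.5% | 9.0% |
| 2, 2 | 1.2% | 2.8% |

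Using observed scans only, rejection stays between 4.8% and 5.2% in all these settings. With a true difference of 3 points (-5 against -2) and 2 of 11 missing in each arm, the expected LOCF difference is 3 x 9/11 = 2.45. Power falls from 51.3% on observed scans to 40.6% (SD 3), or from 22.7% to 19.5% (SD 5).

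**The case against.** The best defence is that exposure is narrow. SAP 3.4.6 makes the PPS the main efficacy set and the FAS supplementary, and the PPS removes most boys who could lack a Week 24 scan. The LOCF result appears beside the observed-data t-test and an MMRM with baseline as covariate; %MVI also has a version adjusted for age and steroid history. Protocol 13.1.2.2 and SAP 3.4.2 make no imputation the default, with LOCF used as needed. The trial is a feasibility-sized pilot judged on numerical trends, with no multiplicity control. All of this stands and limits severity. It does not make the CT LOCF run informative, and the SAP does not say which result prevails if the runs disagree.

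A reader might go further and infer that imputed zeros shrink the SD and so flatter p-values generally. That does not hold. The variance with a fraction m of zeros is (1 - m) x SD^2 + m x (1 - m) x mu^2. With assumed mu = -5 and m = 2/11:

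- SD 3: 0.818 x 9 + 0.149 x 25 = 11.08, so the SD rises to 3.33.
- SD 5: 0.818 x 25 + 0.149 x 25 = 24.17, so it falls only to 4.92.

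Whether false rejection rises or falls depends on the imbalance in missing scans, and equal missingness makes the test conservative.

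A reader might also call zero the best plausible outcome. The documents describe progression but give no 24-week rate for CT, so favourable is as far as they go. Nor is the carried value invariably baseline: SAP 8.3 would carry an off-schedule scan if one existed. Protocol 5.2.4 lists CT in a block shared by the hospitalisation visits, which could suggest a Week 12 scan, but Table 1 and Section 14.1 fix two time points.

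**Conclusion.** The point holds for CT on the plan's own wording: without an off-schedule scan, a missing Week 24 CT is scored as no change. For 6MWD, the timed tests and muscle strength it holds only for boys with no Week 12 value. It bears mainly on the FAS LOCF t-tests.

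The direction is not fixed. Unequal missingness favours whichever arm loses more scans; equal missingness dilutes a real difference. Under the assumed change of -5 points, with 3 of 11 missing on active only, the spurious benefit is 3/11 x 5 = 1.36 points and false rejection is about 9% to 13.5%, against about 5% on observed scans. These sizes rest on assumed CT means and SDs, 11 boys per arm and missingness at random. The zero itself needs none of those assumptions. Severity is modest: one supplementary run of a secondary endpoint in an exploratory trial, with sounder analyses already planned beside it.

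**What to change.** In SAP 8.3, state that LOCF carries post-baseline values only, that a subject with no post-baseline value stays missing in the LOCF run, and that LOCF is not applied to skeletal muscle CT. Amend SAP 6.2.1(2) and Protocol 13.1.3.3.1(2) to match; changing the SAP alone would leave the two documents in conflict. CT then rests on the observed-data t-test and the baseline-adjusted model, both already specified.

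The cost is one SAP sentence, the matching edit in SAP 6.2.1(2) and a protocol edit by the amendment route in Protocol 16.3. The CT LOCF tables, including their subgroup versions, are dropped. LOCF runs for the other endpoints lose boys with no post-baseline value, so their denominators may be smaller and should be reported by arm.

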## **6.2.2** SAFETY ANALYSIS

The analyses described below will be performed in treated patients for each treatment group. In tabulation of adverse events (adverse drug reactions), System Organ Class (SOC) and Preferred terms (PT) of MedDRA will be used. An exact method based on F distribution will be used for estimation of the confidence interval of incidences.

The adverse events which have occurred or become exacerbated after administration of the investigational product will be tabulated.

## (1) Adverse events

- The incidence of adverse events will be calculated.
- The incidence for each of the following conditions will be calculated.
- Adverse events, severe adverse events, serious adverse events, adverse events leading to suspension of administration, adverse events leading to dose reduction, adverse events leading to discontinuation of this study, and adverse events leading to death
- The incidence of adverse events for each adverse event type according to PT of MedDRA will be calculated. When a same event has occurred several times in a same patient, the event will be regarded as 1 event in tabulation.
- For each adverse event type, the number and proportion of subjects with adverse events will be calculated by severity. When a same event has occurred several times in a same patient, the event will be regarded as 1 event in tabulation. Tabulation of severity will be conducted by extracting 1 event in the priority order of severe, moderate, and then mild.
- For each adverse event type, all adverse events reported from the start of investigational product administration to the end day of the follow-up period will be listed for each subject with the adverse event term, severity, onset date, treatment provided, outcome, date of theoutcome confirmed, causal relationship to the investigational product, and comments on the event.
- (2) Adverse drug reactions
  - For adverse drug reactions, analyses will be performed in the same way as for adverse events.
- (3) Laboratory values

Concerning Mg, the data collected by using the unit of mEq/L will be converted to the unit of mg/dL by the following formula before analysis.

Mg concentration after conversion  $(mg/dL) = 1.2 \times Mg$  concentration before conversion (mEq/L)

- For each laboratory parameter, summary statistics at each evaluation time point will be calculated.
- For each laboratory parameter, the time course of each measured value will be plotted for each subject.

## (4) 12-lead ECG

For QTc interval, a test parameter of 12-lead ECG, Fridericia's formula will be used.

- For QTcF interval and heart rate, summary statistics of measured values at each evaluation time point will be calculated.
- For QTcF interval and heart rate, summary statistics of the change from immediately before Day 1 dose in measured values at each evaluation time point after start of the dose will be calculated.
- The QTcF interval at each evaluation time point will be categorized into "≤450 msec, > 450 msec and ≤480 msec, > 480 msec and ≤500 msec, and > 500 msec" before frequency tabulation.
- The change in QTcF interval from the value immediately before Day 1 dose to each time point of evaluation will be categorized into "≤30 msec, > 30 msec and ≤60 msec, and > 60 msec" before frequency tabulation.

- The proportion of subjects with abnormal change in 12-lead ECG (patients for whom the result is judged to be "Abnormal with clinical significance") and the 2-sided 95% confidence interval will be calculated. A list of subjects with abnormal change in 12-lead ECG will also be created.
- (5) Body weight, blood pressure, pulse rate, and body temperature
  - For body weight, systolic blood pressure, diastolic blood pressure, pulse rate, and body temperature (axilla), summary statistics at each evaluation time point will be calculated.
  - For body weight, blood pressure and pulse rate, summary statistics of the change from immediately before Day 1 dose at each evaluation time point will be calculated.
- (6) Cardiac ultrasonography (echocardiography)
  - For left ventricular EF and left ventricular FS, summary statistics at each evaluation time point will be calculated.
  - For left ventricular EF and left ventricular FS, summary statistics of the change from the baseline value measured in the screening period at each evaluation time point will be calculated.
  - The incidence of the cases with abnormalities on echocardiography (patients for whom Clinical Significance was judged to be "Yes") and 2-sided 95% confidence interval will be calculated.

## **6.3** Analyses of Pharmacodynamic and Exploratory Endpoints

The following analyses will be performed for urinary excretion of tetranor-PGDM/-PGEM, urine tetranor-PGDM/Cre concentration ratio, urine tetranor-PGEM/Cre concentration ratio, urinary creatinine excretion, urinary creatine excretion, and creatine in urine (%) in the PPS and FAS: Analysis will also be conducted in the group combining the low-dose group and the high-dose group excluding the analysis of MMRM and charts.

For the method to derive each endpoint, refer to Table 10.2. Method to Derive Pharmacodynamic Endpoints and Exploratory Endpoints.

- Summary statistics at each time point will be calculated for each treatment group.
- Summary statistics of the change rate from baseline at each time point will be calculated, followed by a 2-sample t-test between each treatment group and placebo group at each time point. If the data at Week 24 are missing, conduct analyses with and without the LOCF imputation.
- With respect to the above 2 analyses, subgroup analysis of the following items will be conducted for urinary tetranor-PGDM/creatinine concentration ratio in the PPS.
  - Subgroup analysis: Baseline 6MWD (<350 m, and  $\geq 350 \text{ m}$ )
- The treatment effect will be estimated using the MMRM. The changes from baseline in the values measured at other time points will also be included in this analysis. Covariates will be the assigned group, baseline value, time point, and the interaction term of the assigned group and time point.
- Using the MMRM, the dose relationship will be analyzed with treatment contrasts of (placebo group, low-dose group, high-dose group) = (-2 1 1), (-1 0 1), and (-1 -1 2). Covariates will be the assigned group, baseline value, time point, and the interaction term of the assigned group and time point.
- With respect to the above 2 analyses, subgroup analysis of the following items will be conducted for urinary tetranor-PGDM/creatinine concentration ratio in the PPS.
  - Subgroup analysis: Baseline 6MWD (<350 m, and  $\geq 350 \text{ m}$ )
- The correlation coefficients (Pearson and Spearman) with the change from baseline in each item specified in (1) and (2) of Section 6.2.1 will be calculated for the change rate from

baseline at each time point in each treatment group and the group combining all groups. In addition, scatter plots of pharmacodynamic endpoints will be generated for each group by plotting the change rates of urinary tetranor-PGDM excretion, urinary tetranor-PGEM tetranor-PGDM/creatinine excretion. urinary concentration ratio. and urinary tetranor-PGEM/creatinine concentration ratio from baseline to Week 24 along the horizontal axis, and the changes at Week 24 along the vertical axis. Moreover, scatter plots of exploratory endpoints will be generated by plotting the change rates of urinary creatinine excretion, urinary creatine excretion, and % creatine urine from baseline to Week 24 along the horizontal axis, and the changes in 6MWD and muscle volume (skeletal muscle CT) from baseline to Week 24 along the vertical axis.

The time course by each time point will be plotted for each treatment group. Similarly, charts showing the time course of the change rates from baseline for urinary tetranor-PGDM excretion, urinary tetranor-PGEM excretion, urinary tetranor-PGDM/creatinine concentration ratio, and urinary tetranor-PGEM/creatinine concentration ratio in the PPS will be generated.

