# 13.1.3.4 Analyses of Pharmacodynamic and Exploratory Endpoints

The following analyses will be performed for urinary excretion of tetranor-PGDM/-PGEM, urine tetranor-PGDM/Cre concentration ratio, urine tetranor-PGEM/Cre concentration ratio, urinary creatinine excretion, urinary creatine excretion, and creatine in urine (%) in the PPS and FAS:

- Summary statistics at each time point will be calculated for each treatment group.
- Summary statistics of the change rate from baseline at each time point will be calculated, followed by a 2-sample t-test between each treatment group and placebo group at each time point. This analysis will be performed with and without the LOCF imputation.
- The treatment effect will be estimated using the MMRM.
- Using the MMRM, the dose relationship will be analyzed with treatment contrasts of (placebo group, low-dose group, high-dose group) = (-2 1 1), (-1 0 1), and (-1 -1 2).
- The correlation coefficient (Pearson, Spearman) between the change rate from baseline at each time point in each treatment group and the change from baseline in each item specified in (1) and (2) of Section 13.1.3.3.1 will be calculated.
- The time course by each time point will be plotted for each treatment group.

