## 2. Target Sample Size and Rationale for the Sample Size

Target sample size: a total of 33 subjects (11 subjects for each group)

Given that DMD is a rare disease that allows only limited recruitment of subjects and that this study is primarily intended to evaluate the efficacy of TAS-205 in an exploratory manner, the sample size was determined not statistically, but based on feasibility.

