  - For each group and the group combining all groups, summary statistics of baseline %MVI (%) in both legs will be calculated.
  - For each group, summary statistics of baseline %MVI (%) will be calculated, and 2-sample t-test between groups will be performed. In addition, subgroup analysis will be conducted for the following items.
    - Subgroup analysis: Baseline 6MWD (<350 m, and ≥350 m)
  - For the group combining all groups, the correlation coefficients (Pearson and Spearman) of each %MVI (%) at baseline will be calculated.
  - For each group and the group combining all groups, the correlation coefficients (Pearson and Spearman) of the changes in the %MVI (%) in both legs at Week 24 and the change rates of urinary tetranor-PGDM/creatinine concentration ratio and urinary tetranor-PGDM on Day 168, and P values for the correlation coefficients will be calculated. In addition, subgroup analysis will be conducted for the following items.

Subgroup analysis: Baseline 6MWD ( $\leq$ 350 m, and  $\geq$ 350 m)

Analysis of covariance will be performed using the following variables as conditions.
 Objective variables: Changes in %MVI (%) in both legs at Week 24
 Explanatory variables: Baseline %MVI (%) in both legs, age, presence or absence of the history of steroid use, baseline urinary tetranor-PGDM/creatinine concentration ratio, and the change rate of urinary tetranor-PGDM/creatinine concentration ratio on Day 168
 In addition, subgroup analysis will be conducted for the following items.

Subgroup analysis: Baseline 6MWD (<350 m, and ≥350 m)

- (3) Pharmacodynamic Endpoints
  - For each group and the group combining the low-dose group and the high-dose group, summary statistics of the change rates of urinary tetranor-PGDM excretion, urinary tetranor-PGEM excretion, urinary tetranor-PGDM/creatinine concentration ratio, and urinary tetranor-PGEM/creatinine concentration ratio will be calculated at each time point, and 1-sample t-test using the change rate = 0% as null hypothesis will be conducted at each time point. In addition, subgroup analysis will be conducted for the following items.

Subgroup analysis: Baseline 6MWD (<350 m, and ≥350 m)

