#### run;

- ATRTN: Treatment group (placebo group [reference group], low-dose group, high-dose group)
   AVISITN: Time point (Week 12, Week24)
  - SUBJID: Patient ID

AVAL: Response variable

BASE: Baseline value

- Contrast coefficient (-2 1 1): Paired comparison of low-dose group saturation Contrast coefficient (-1 0 1): Paired comparison of linear trend Contrast coefficient (-1 -1 2): Paired comparison of high-dose group saturation
- # If convergence is not achieved with UN, TOEP will be used. If convergence is not achieved yet, the following will be used in this order:  $AR(1) \rightarrow CS \rightarrow VC$ .

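### PD endpoints: SAP 6.3 words the t-tests and the MMRM on different scales and, separately, the exploratory 1-sample test in SAP 6.6(3) uses a 0% null that is off centre

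*SAP*

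**What the plan says.** **T-tests.** For the urinary PGDM, PGEM, creatinine and creatine endpoints, SAP 6.3 states: "Summary statistics of the change rate from baseline at each time point will be calculated, followed by a 2-sample t-test". The comparison is each dose against placebo. Protocol 13.1.3.4 prescribes the same change rate for the t-test and for the correlations with efficacy.

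**MMRM.** Later in SAP 6.3 the model for the same endpoints is described with: "The changes from baseline in the values measured at other time points will also be included in this analysis". The dose contrasts use the same model. SAP 6.2.1(2) has the same sentence for efficacy endpoints, which are analysed as change. The notes to the SAS code in SAP 8.3 give only "AVAL: Response variable". Protocol 13.1.3.4 says "The treatment effect will be estimated using the MMRM" and names no scale.

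**1-sample test.** SAP 6.6(3), in the PPS, covers the four PGDM and PGEM endpoints: "1-sample t-test using the change rate = 0% as null hypothesis will be conducted at each time point". It applies as follows: "For each group and the group combining the low-dose group and the high-dose group".

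Neither document mentions a log transformation of these endpoints or gives a variability for them.

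**The concern.** There are two separate defects, and neither follows from the other.

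1. **Scale.** The SAP uses change rate and change as different terms. Its correlation bullet in 6.3 pairs the change rate of a PD endpoint with the change of an efficacy endpoint. Read in that sense, the t-test result is in percentage points, while the MMRM estimates and dose contrasts are in ng, g or concentration ratio. The two cannot be set side by side. Absolute change also suits these data poorly: Protocol 4.1 admits boys from 7.5 kg to under 60 kg, and Protocol 1.1 notes that PGDM excretion is reported to rise with age. The same proportional inhibition would therefore give very different absolute falls.

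2. **Null.** Percent change divides by a baseline that is itself measured with variation. Its mean is above zero when nothing has changed, so 0% is not the no-effect value for the test in 6.6(3).

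What is at stake is how the drug's effect on PGD2 production is read. Protocol 8.4 gives this as the purpose of the PD analysis, and Protocol 2.3 lists the effect on PGDM excretion among the exploratory objectives.

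**Working it through.** **Inputs.** 11 boys per group, so 22 in the combined dose group (SAP 2; the PPS may be smaller). The plan has no power or SD for these endpoints, so there is no figure of its own to reproduce. Assumptions: lognormal values; within-boy log-SD s from 0.1 to 0.5; 2-sided 5% tests, since the SAP sets no level for these t-tests.

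**Why 0% is off centre.** If baseline X and post-dose Y are positive and exchangeable (no true change), then E[Y/X] = E[(Y/X + X/Y)/2] ≥ 1, with equality only if there is no within-boy variation. This needs no assumed SD.

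**Size.** For lognormal values and a true ratio r (0.7 for a 30% fall):

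- Within an arm, mean change rate = r × exp(s²) − 1.
- Against placebo, difference = [r × exp(s²) − 1] − [exp(s²) − 1] = (r − 1) × exp(s²).

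Example at s = 0.3: exp(0.09) = 1.094. With no change the mean is +9.4%. With r = 0.7 it is 0.7 × 1.094 − 1 = −23.4%. The difference from placebo is −0.3 × 1.094 = −32.8 points.

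| s | No change, within arm | True 30% fall, within arm | True 30% fall, minus placebo |
|---|---|---|---|
| 0.1 | +1% | −29% | −30 points |
| 0.2 | +4% | −27% | −31 points |
| 0.3 | +9% | −23% | −33 points |
| 0.4 | +17% | −18% | −35 points |
| 0.5 | +28% | −10% | −39 points |

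**Error rates and power.** From 200,000 simulated trials per setting, with log ratio ~ Normal(ln r, 2s²). Power is for a true 40% fall.

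| s | 1-sample, n = 11: two-sided error, percent change | 1-sample, n = 11: power, percent change / log ratio | 1-sample, n = 22: false increases (nominal 2.5%) | 2-sample, 11 v 11: power, percent change / log ratio |
|---|---|---|---|---|
| 0.1 | 5.0% | 100% / 100% | 3.9% | 100% / 100% |
| 0.2 | 5.2% | 99.8% / 100% | 6.0% | 97.5% / 98.0% |
| 0.3 | 5.4% | 88% / 95% | 8.6% | 73% / 77% |
| 0.4 | 5.7% | 61% / 77% | 11.8% | 46% / 52% |
| 0.5 | 6.0% | 38% / 58% | 15.1% | 29% / 36% |

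On the log ratio the 1-sample test holds its error at 4.9% to 5.1% at both sizes. The 2-sample test on percent change has a centred null: with no effect it rejects in 5.0% of trials at s = 0.1, falling to 4.2% at s = 0.5.

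**Scale difference.** If every boy has a 30% fall, the absolute fall is proportional to his baseline. The ratio of its 90th to 10th percentile is exp(2 × 1.2816 × σ), with σ = √ln(1 + CV²). For an assumed between-boy baseline CV of 30%, σ = 0.294 and the ratio is 2.1. For 50%, σ = 0.472 and the ratio is 3.4.

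**The case against.** The strongest case on the other side has five parts.

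- **Absolute change is not stated.** The sentence in 6.3 mainly says that other time points enter the model, and it may have been carried over from 6.2.1. This stands: a reader might infer that the MMRM is specified on absolute change, but that is only the natural reading. The alternative is a response with no stated scale, which needs the same repair.
- **The bias is not towards zero throughout.** A reader might infer that the plan understates inhibition in general. The documents do not support that. Shrinkage applies to an arm read alone. The test in 6.3 is against placebo, where the bias under no effect cancels and a true fall is slightly overstated in percentage points. Its power loss is about 4 to 7 points at log-SD 0.3 to 0.5.
- **The 0% null is narrow.** It appears only in the exploratory PPS test of 6.6(3), not in 6.3. Placebo is tested there too, so upward drift could be seen. At 11 per group the false-decrease tail is below its nominal 2.5%, which is conservative for claiming inhibition. All this stands. It does not help the combined dose group, where false increases do accumulate, or recover the lost power.
- **The size is assumed.** This stands. At log-SD 0.1 the effect is negligible, and at 0.2 or less power for a 40% fall differs by under one point.
- **Significance is not the aim.** Protocol 14.1 relies on numerical trends, and the sample size was set on feasibility. That lowers the weight of the power figures. But a trend read from within-arm mean change rates is itself shifted.

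**Conclusion.** Both defects hold, each within limits. As worded, SAP 6.3 puts the PD t-tests and the PD MMRM on different scales and leaves the MMRM response undefined. The 0% null in 6.6(3) is off centre upward whenever values vary within a boy. That direction is mathematical; the amount depends on a log-SD that the documents do not give. It runs from trivial at 0.1 to a null mean of +28% at 0.5, where within-arm power for a 40% fall is 38% instead of 58% and false increases in the combined dose group reach about 15%.

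The placebo comparison in 6.3 remains valid as a test. The analyses concerned are pharmacodynamic and exploratory, with no multiplicity control (SAP 3.4.5). The primary endpoint, change in 6MWD at Week 24, is not affected. The point is worth correcting before unblinding, because an undefined response otherwise leaves the scale open to choice once results are known.

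**What to change.** - In SAP 6.3 and 8.3, define AVAL for the PD MMRM as log(post/baseline), with log baseline as covariate.
- Use the same response for the t-tests in 6.3 and for the 1-sample test in 6.6(3), with log ratio = 0 as the null.
- Back-transform estimates and intervals to geometric mean percent change. Keep raw change rates as descriptive output.
- Use the log ratio in the Pearson correlations and analyses of covariance that now take the PD change rate. Spearman coefficients do not change, because the log ratio is a monotone function of the change rate.
- Protocol 13.1.3.4 names change rate for the t-test and correlations. Either record the change from the protocol or keep the change-rate t-test as a supporting analysis.

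**Cost.** No new data are needed. Geometric rather than arithmetic mean change is reported, and there is either a documented departure from the protocol wording or a duplicate analysis. A log needs positive values, so the SAP should also say how any result below the assay limit is handled.
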